19.3 Appendix 3: Baseline Diet Assessment

Instructions: To be completed by Study Personnel, through direct interview with Study Participant. Please ask questions to Study Participants, much as they appear below. This assessment should be conducted on Day 1 of screening. This assessment asks about symptoms of eosinophilic duodenitis (EoD).

1. **Are you on Specific, Doctor-Prescribed Diet?** Yes No

If Yes, what is the diet?

Elemental [If ticked-enteral/tube feeding?] Yes No

6-food or 3 Food Elimination Diet

Supplemental Protein Shake/drink specify: _____

Other; describe: _____

2. **Do you have any confirmed food allergies (i.e., confirmed by skin-prick testing or blood tests)?** Yes No

If Yes, what are they? _____

3. **Does eating certain foods seem to make your EoD symptoms worse?** Yes No

If Yes, what are the 3 specific foods/types of foods that make the effects worse?

Food or Type of Food	Effect

4. **Do you avoid eating any specific foods or types of foods due to your EoD symptoms?** Yes No

If Yes, which foods are **always** avoided? _____

5. **Do you avoid? (tick all that are appropriate)**

Milk Egg Wheat Soy

What are the main foods that YOU DO eat?

If a full diet is eaten do not list all types of foods, just write "All foods."

6. **Do you avoid eating at certain times of the day to avoid symptoms of EoD?** Yes No

If Yes, please describe: _____

19.4 Appendix 4: Common Terminology Criteria for Adverse Events (version 5.0)

The CTCAE (version 5) for download can be found at:

https://ctep.cancer.gov/protocolDevelopment/electronic_applications/docs/CTCAE_v5_Quick_Reference_5x7.pdf

Example of Grading for Infusion-Related Reactions

Adverse Event	General Disorders and Administration Site Conditions				
	Grade 1	Grade 2	Grade 3	Grade 4	Grade 5
Infusion-related reaction	Mild transient reaction; infusion interruption not indicated; intervention not indicated	Therapy or infusion interruption indicated but responds promptly to symptomatic treatment (e.g., antihistamines, NSAIDS, narcotics, IV fluids); prophylactic medications indicated for ≤ 24 hours	Prolonged (e.g., not rapidly responsive to symptomatic medication and/or brief interruption of infusion); recurrence of symptoms following initial improvement; hospitalization indicated for clinical sequelae	Life-threatening consequences; urgent intervention indicated	Death

Definition: A disorder characterized by adverse reaction to the infusion of pharmacological or biological substances.

Example of Grading for Laboratory Abnormalities

Adverse Event	Grade				
	1	2	3	4	5
Growth hormone abnormal	Asymptomatic; clinical or diagnostic observations only; intervention not indicated	Symptomatic; medical intervention indicated; limiting instrumental ADL	–	–	–
Definition: A finding based on laboratory test results that indicate abnormal levels of growth hormone in biological specimen.					
Haptoglobin decreased	<LLN	–	–	–	–
Definition: A finding based on laboratory test results that indicate a decrease in levels of haptoglobin in a blood specimen.					
Hemoglobin increased	Increase in >0 –2 g/dL	Increase in >2 –4 g/dL	Increase in >4 g/dL	–	–
Definition: A finding based on laboratory test results that indicate increased levels of hemoglobin above normal.					
Lipase increased	$>\text{ULN} - 1.5 \times \text{ULN}$	>1.5 –2.0 \times ULN; >2.0 –5.0 \times ULN and asymptomatic	>2.0 –5.0 \times ULN with signs or symptoms; $>5.0 \times \text{ULN}$ and asymptomatic	$>5.0 \times \text{ULN}$ and with signs or symptoms	–
Definition: A finding based on laboratory test results that indicate an increase in the level of lipase in a biological specimen.					
Lymphocyte count decreased	$<\text{LLN} - 800/\text{mm}^3$; $<\text{LLN} - 0.8 \times 10\text{e}9/\text{L}$	<800 –500 mm^3 ; <0.8 –0.5 $\times 10\text{e}9/\text{L}$	<500 –200 mm^3 ; <0.5 –0.2 $\times 10\text{e}9/\text{L}$	$<200/\text{mm}^3$; $<0.2 \times 10\text{e}9/\text{L}$	–
Definition: A finding based on laboratory test results that indicate a decrease in number of lymphocytes in a blood specimen.					
Lymphocyte count increased	–	$>4000/\text{mm}^3$ – $20,000/\text{mm}^3$	$>20,000/\text{mm}^3$	–	–
Definition: A finding based on laboratory test results that indicate an abnormal increase in the number of lymphocytes in the blood, effusions or bone marrow.					

19.5 Appendix 5: EGD and Colonoscopy Histology

Details for collecting, labeling, and shipping specimens will be provided separately in the Histology Manual.

Staining: The performance of the evaluations listed below will require the following stains for each biopsy set:

- Esophagus: 1) H&E; 2) tryptase; 3) trichrome

For patients with a history of EoE and/or with a score of ≥ 3 on the dysphagia question during screening, esophageal biopsies will also be collected at screening and postdose.

- Stomach: 1) H&E; 2) tryptase
- Duodenum: 1) H&E; 2) tryptase
- Colon: 1) H&E; 2) tryptase

Biopsies will be obtained from the following:

- **Esophagus** (if patient has a history of concomitant EoE, if esophagus looks suspicious for EoE, or if patient is symptomatic on screening dysphagia question, quantified by a score of >3 on the dysphagia question on at least 1 day during screening).

- A set of 2 fragments from the distal esophagus
- A set of 2 fragments from the mid-proximal esophagus
- Up to 2 extra specimens may be collected if there are any additional areas of interest.

A count of ≥ 15 eosinophils/hpf in at least 1 esophageal site will be considered diagnostic of EoE for the purposes of the study.

- **Stomach**

- 4 specimens from separate areas of the gastric antrum (2–5 cm proximal to the pylorus)
- 4 specimens from separate areas of the gastric corpus (2 from the proximal lesser curvature and 2 from the greater curvature)
- Up to 2 extra specimens may be collected if there are any additional areas of interest.
- 1 fragment will be collected for exploratory analysis (shipped to Allakos directly).

19.5 Appendix 5: EGD and Colonoscopy Histology cont.

- **Duodenum**
 - 4 fragments of duodenal mucosa from the second and third part of the duodenum
 - Up to 2 extra specimens may be collected if there are any additional areas of interest.
 - 1 fragment will be collected for exploratory analysis (shipped to Allakos directly).
- **Colon**
 - At least 2 fragments (preferably 3 fragments) each from terminal ileum; ascending, transverse, descending, and sigmoid colon; and rectum
 - Up to 2 extra specimens may be collected if there are any additional areas of interest.
 - 1 fragment each will be collected from terminal ileum; ascending, transverse, descending, and sigmoid colon; and rectum for exploratory analysis (shipped to Allakos directly).

The following will be reported for esophageal biopsies:

- Maximum number of eosinophils/hpf
- Maximum number of tryptase-positive mast cells/hpf

The following histopathologic parameters will be graded from 0 (absent) to 3 (marked or severe):

- Eosinophilic microabscesses
- Eosinophilic degranulation
- Basal zone hyperplasia
- Spongiosis
- Subepithelial tissue present (Y/N)
- *Lamina propria* fibrosis: (grade only if subepithelial tissue is present)

The following will be reported for gastric biopsies:

- A highly sensitive monoclonal immunohistochemical stain will be used. The following histopathologic parameters will be graded using the Updated Sydney System from 0 (absent) to 3 (marked or severe):
 - Active inflammation
 - Chronic inflammation

19.5 Appendix 5: EGD and Colonoscopy Histology cont.

- Intestinal metaplasia
- Atrophy
- Reactive gastropathy
- Eosinophil and mast cell counts will be reported as:
 - Maximum number of eosinophils/hpf in at least 5 hpf on each biopsy fragment
 - Maximum number of tryptase-positive mast cells/hpf in at least 5 hpf on each biopsy fragment

The following will be reported for duodenal biopsies:

- Eosinophil and mast cell counts will be reported as:
 - Maximum number of eosinophils/hpf in at least 3 hpf on each biopsy fragment
 - Maximum number of tryptase-positive mast cells/hpf in at least 3 hpf on each biopsy fragment
- Duodenal intraepithelial lymphocytosis (with counts per 100 enterocytes when count is >20)
- Villous architecture

The following will be reported for ileal and colonic biopsies:

- Eosinophil and mast cell counts will be reported as:
 - Maximum number of eosinophils/hpf in at least 5 hpf on each biopsy fragment
 - Maximum number of tryptase-positive mast cells/hpf in at least 5 hpf on each biopsy fragment
- In addition, the ileal and colonic biopsies will be evaluated for chronic or active inflammation, lymphocytic colitis, collagenous colitis, or evidence of inflammatory bowel disease. The presence of any of these abnormalities will be reported by the central reader and evaluated against eligibility criteria by the Investigator and Allakos Medical Monitor.

Any stored tissue from biopsies of the esophagus, stomach, duodenum, or ileum may be used for exploratory analysis.

19.6 Appendix 6: Sampson's Criteria of Anaphylaxis

ANAPHYLAXIS: Sampson's definition of anaphylaxis (clinical definition) is the acute onset of illness (minutes to several hours) which involves **SKIN, MUCOSAL TISSUE, or BOTH** (e.g., generalized hives, pruritus or flushing, swollen lips-tongue uvula) **with 1 OR more of the following** (Sampson, 2006):

- **RESPIRATORY:** Airway compromise (e.g., dyspnea, wheeze, or bronchospasm, stridor, reduced PEF, hypoxemia)
- **CIRCULATORY:** Reduced blood pressure or associated symptoms of end-organ dysfunction (e.g., hypotonia, syncope)

OR

2 or MORE of the following that occur rapidly after exposure:

- **SKIN, MUCOSAL TISSUE:** e.g., generalized hives, itch-flush, swollen lips-tongue-uvula
- **RESPIRATORY:** Airway compromise (e.g., dyspnea, wheeze, or bronchospasm, stridor and reduced PEF)
- **CIRCULATORY:** Reduced blood pressure or associated symptoms of end-organ dysfunction (e.g., hypotonia, syncope)
- **GASTROINTESTINAL:** Persistent gastrointestinal symptoms (e.g., crampy abdominal pain, vomiting, nausea, diarrhea)

19.7 Appendix 7: ePRO Teaching Tool for Study AK002-021

INSTRUCTIONS FOR COMPLETION OF ELECTRONIC QUESTIONNAIRES

You are being asked to complete a ONCE DAILY 10-question EG/EoD questionnaire about your current symptoms, as well as other questionnaires as specified on page 3.

WEBSITE: <https://v4me.viedoc.net>

TO ACCESS THE ELECTRONIC QUESTIONNAIRES

- You MUST have access to the Internet in order to use the website (ViedocME) to complete the daily questionnaires. Let your study coordinator know if you expect this will be a problem for you.
- You MAY access the website from a *computer, smart-phone, tablet, or other device* with Internet service. Different devices may be used on different days to log into ViedocME and complete the questionnaires.
- The daily PRO questionnaire SHOULD BE COMPLETED around the same time each day and must be completed by 11:59PM at the latest, each day (based on your time zone). If you miss a daily questionnaire (i.e. it is not completed by 11:59PM), it will not be available for completion at a later time. It is very important to remember to complete the daily questionnaire by 11:59PM every day.
- If you miss a daily questionnaire, the next day's questionnaire will still populate. Continue answering any future questionnaires and remember to only recall your symptoms over the last 24 hours (1 day).
- During the entire duration of the study, you will answer the EG/EoD PRO questionnaire and one additional question each, for "Dysphagia" and "Constipation".

ViedocMe

LOGGING IN TO VIEDOCME

User

←

Key

←

Log in

Enter 6-digit Username provided by Study Coordinator

Enter 4-digit PIN provided by Study Coordinator

If you forget your Username or your PIN please contact the Study Coordinator to provide/reset for you. The PIN can be reset but will not be saved by the site as you are the only one who should have access to this.

ViedocMe 4.42
 (2018-05-28 04:27:15 UTC)

[figure not shown]
REMINDERS FROM VIEDOCME FOR COMPLETION OF DAILY QUESTIONNAIRES

- When the Study Coordinator sets up your ViedocME account you can choose to receive a DAILY reminder to complete your questionnaire(s) for the day. The reminder(s) will be sent if you diary entry has not been completed by 8PM each evening (in your study site time zone).
- The ViedocME reminders can be sent via Text Message and/or Email
- *If you are Roaming outside your service area or your telephone carrier charges you per text message, please be aware that you may incur charges for receiving text messages. If you prefer, the Study Coordinator can help you set up a daily alarm reminder on your personal cellular device that will ring as an alarm.*

[figure not shown]
Appendix 7: ePRO Teaching Tool cont.

THINGS TO REMEMBER WHEN USING THE ELECTRONIC QUESTIONNAIRES

- When you first log on to ViedocME the HOME screen will display the 1st questionnaire that is due for the day, which is usually the 10-question PRO questionnaire as shown below:

- Click SEND when you have answered all 10 questions on the daily EG/EoD PRO questionnaire:

- You will daily complete one additional question each, about dysphagia (difficulty swallowing) and constipation following the completion of the 10 question ePRO questionnaire.
- On study visit days you will access ViedocME to complete the SF-36 Health Survey.
- On screening Day 19 and study days 7, 28, 225 and ET, you will complete the 1-question PGIS via ViedocME.
- On study days 7, 28, 225, and ET, you will complete the 1-question PGIC via ViedocME.

COMPLETING THE DAILY QUESTIONNAIRES DURING THE STUDY

You will complete the EG/EoD questionnaire, and the additional questions during the entire duration of the study:

- SCREENING period (BEFORE you receive 1st study drug)
- TREATMENT period (WHILE you are receiving study drug)
- FOLLOW UP period (AFTER you have received all study drug or at the last study visit)

During the screening period, the questionnaire is used to determine if your symptoms are appropriate in type and intensity to be enrolled into the study.

Patients with a history of EoE and/or with a score of ≥ 3 on the dysphagia question during screening will also have esophageal biopsies collected during the EGD at screening and postdose.

You will start completing the daily questionnaires (EG/EoD daily questionnaire, and the additional questions) on the first day of your participation in this study and will complete the questionnaires until your last day of participation in this study.

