Table 1 Study AK002-016 in Subjects with Moderate-to-Severe EG/EoD: Co-Primary Endpoints of Histology and Symptoms

Co-Primary Endpoint	Lirentelimab (n=89)	Placebo (n=91)
Co-Primary Endpoint – Histology		
Histology Endpoint: Proportion of responders as determined by gastric or duodenal tissue eosinophil count ¹	84.6%	4.5%
p-value	<0.001	–
Co-Primary Endpoint – Symptoms		
Baseline TSS	29.5	27.57
Symptom Endpoint: Absolute mean change in subject reported TSS ²	-10.0	-11.5
p-value	0.343	–

- 1) A responder is a subject achieving the following peak eosinophil counts: eosinophil count ≤ 4 cells/hpf in 5 gastric hpf and/or eosinophil count ≤ 15 cells/hpf in 3 duodenal hpf. Endpoint assessed at end of Week 24.
- 2) TSS6 is a daily PRO questionnaire assessing 6 symptoms (abdominal pain, nausea, bloating, early satiety, abdominal cramping, and loss of appetite) on a scale from 0 to 10. Endpoint was assessed as mean change from baseline to Weeks 23–24.

When the change in TSS6 was analyzed for the Phase 3 AK002-016 study subjects enrolled at the sites that also participated in the Phase 2 AK002-003 study, the effect size as well as statistical significance for lirentelimab over placebo were consistent with the AK002-003 study (Figure 1). In contrast, when mean changes in TSS6 were analyzed separately for the Phase 3 AK002-016 sites who did not participate in the Phase 2 AK002-003 study, there was no separation between lirentelimab and placebo for subject symptom scores.

Left: Phase 2 Study AK002-003; Right: Phase 3 Study AK002-016 Sites that participated in AK002-003. Least squares means and p-values derived from ANCOVA/MMRM models.

Figure 1 Effects Observed in Subjects at Clinical Sites that Participated in Both AK002-003 and AK002-016 Studies

The proposed dose regimen of 6 total doses of 3 mg/kg AK002, administered every 4 weeks, is based on experience with AK002 in healthy volunteers and in patients with ISM, CU, severe AC, mast cell disease, EoE, and EG/EoD. The proposed dose of 3 mg/kg is based on experience across multiple prior studies, in which subjects received 60 mg prednisone as premedication followed by a dose of 3 mg/kg AK002 for the first infusion. This dosing regimen was well tolerated. By using this premedication regimen, the incidence and severity of IRR were substantially reduced.

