7.4 Inclusion Criteria

Patients are eligible to enroll in the study if all of the following criteria are met:

- 1) Provide written informed consent.
- 2) Male or female aged ≥ 18 and ≤ 80 years at the time of signing the informed consent for entry.
- 3) Baseline endoscopic biopsy with ≥ 30 eosinophils/hpf in at least 3 hpf in the duodenum as determined by central histology assessment of biopsies collected during the screening EGD without any other significant cause for the eosinophilia.
- 4) Completion of at least 4 daily PRO questionnaires per week for a minimum of 3 weeks during screening.
- 5) A weekly average score of abdominal pain, nausea, or diarrhea ≥ 3 on the PRO questionnaire (score from 0–10) for at least 2 weeks of screening and a weekly average TSS of ≥ 10 for at least 2 weeks of screening.
- 6) Inadequate or loss of response to, or intolerant to standard therapies for EoD symptoms, which could include PPI, antihistamines, systemic or topical corticosteroids, and/or diet, among others.
- 7) If patient is on pre-existing dietary restrictions, willingness to maintain dietary restrictions throughout the study.
- 8) Willing and able to comply with all study procedures and visit schedule including follow-up visits.

9) Female patients must be either post-menopausal for at least 1 year with FSH level >30 MIU/mL at screening or surgically sterile (tubal ligation, partial or total hysterectomy, or bilateral oophorectomy) for at least 3 months or, if of childbearing potential, have a negative pregnancy test and agree to use dual methods of contraception, have a partner who had a vasectomy, or agree to abstain from sexual activity from screening until the end of the study, or for 120 days following last dose of study drug, whichever is longer.

Non-vasectomized male patients with female partners of childbearing potential must agree to either abstain from sexual activity or agree to use a highly effective method of contraception from screening until the end of the study or for 120 days following last dose of study drug, whichever is longer. All fertile men with female partners of childbearing potential should be instructed to contact the Investigator immediately if they suspect their partner might be pregnant (e.g., missed or later menstrual period) at any time during study participation.

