10.2 Stratification and Randomization

To be randomized into the study, a patient must have a weekly average score of ≥ 3 (on a scale from 0–10) recorded for either abdominal pain, nausea, and/or diarrhea on the PRO questionnaire for at least 2 weeks during screening and an average weekly TSS ≥ 10 for at least 2 weeks during screening. Completion of at least 4 daily PRO questionnaires per week, for a minimum of 3 weeks during screening, is required to qualify. Patients will be randomized through the Interactive Response Technology (IRT) system.

If the patient qualifies for the study after completing all of the screening procedures on the day prior to or on the day of the first infusion (Study Day 1), the site will access the IRT system in order to stratify and randomize the patient in the study and enter the current body weight for study drug dose calculation. The site will enter the highest weekly TSS of disease activity recorded during the screening period in order to stratify patients into screening TSS < 28 or ≥ 28 strata. The IRT system will then randomly assign the patient at a 1:1 allocation ratio to AK002 3 mg/kg for 6 doses, or placebo in a double-blind manner and will send an email to the pharmacist and/or designee detailing the kit number(s) to use to prepare the infusion.

Approximately 40 patients will be randomized to treatment with AK002 at a dose of 3 mg/kg for 6 doses, and approximately 40 patients will be randomized to placebo. A minimum number of approximately 80 patients with EoD without EG will be enrolled.

A patient is considered enrolled in the study when the patient is randomized.

For subsequent infusions on Days 29, 57, 85, 113, and 141, the coordinator will access the IRT on the day of infusion and enter the PID as well as the patient's body weight, and the system will assign the patient the dose according to their randomization number. The pharmacist and/or designee will then receive an email detailing the kit number(s) to prepare, as well as the volume of study drug to be mixed with NaCl.

Prior to each infusion, the Investigator or designee will confirm the PID recorded on the IV bag provided by the Pharmacist matches the patient. The patient identification should be confirmed and documented by a second party prior to administering the infusion, whenever possible. There will not be any unblinding information on the IRT notification to the Pharmacist or on the infusion bag provided to the site.

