12.1 Screening Period

- 1) Obtain written informed consent.
- 2) Assign the participant a PID.
- 3) Begin the collection of SAE related to any screening activities.
- 4) Collect demographics and medical history.
- 5) Record prior and concomitant medications.
- 6) Determine body weight and height.
- 7) Activate patient access to the ePRO questionnaire portal and instruct patient on use of the website to complete the questionnaire(s). Use the ePRO Teaching Tool to instruct the patient on use of the electronic platform (Appendix 7).
- 8) **CCI** [REDACTED] to be completed by the patient.
- 9) Perform baseline diet assessment.
- 10) Complete previous treatments and procedure review.
- 11) Obtain vital signs before blood draws and after patient at rest ≥ 5 minutes.

- 12) Perform a complete physical examination.
- 13) Obtain a 10-lead or 12-lead ECG before blood draw.
- 14) Collect the following samples for the central laboratory:
 - a) Blood for CBC with differential
 - b) Blood for Chemistry (sample to be tested for FSH and hCG if patient is of childbearing potential)
 - c) Urinalysis
 - d) Blood for serology testing (includes *Strongyloides stercoralis*)
 - e) Blood for PK
 - f) Blood for ADA
 - g) Blood for total serum IgE
- 15) Provide patient a stool collection kit and ask patient to provide a stool sample while on site or return it to the site within 1 day of collection.
- 16) Perform a screening EGD and colonoscopy with biopsy following instructions provided by Allakos any time during the screening period. The EGD and colonoscopy should take place on the same day in order to minimize effects of procedure premedication on the PRO scores. Patient should arrive fasting for the EGD procedure as specified by instructions from the EGD provider.
- 17) **CC1** to be completed by the patient on screening Day 19 (not a clinic visit).
- 18) Using results from the central histology reader, confirm that the eosinophil count from the gastric and/or duodenal biopsies qualify the patient for the study and no exclusionary criteria are found on the EGD or colonoscopy.
- 19) Review all ePRO scores. Since the bowel preparations could artificially increase the scores, exclude ePRO scores from the day before and the day of colonoscopy when assessing eligibility criteria.

12.2 Prior to Day 1

The following procedures will be performed prior to Day 1:

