15.6 Efficacy Analysis

15.6.1 Primary Efficacy Endpoint Analysis

The first co-primary endpoint will be analyzed using Fisher's exact test. Patients who experience an ICE, i.e., exit the study prematurely or initiate prohibited or restricted medication, prior to end of Week 24 will be treated as non-responders. Proportion of responders and the associated 95% confidence interval (CI) will be presented for each treatment group. The between-group difference and the associated 95% CI will also be computed and presented. Sensitivity analysis may be carried out using the Cochran-Mantel-Haenszel (CMH) test stratified by the randomization stratification factor (baseline TSS <28 vs ≥ 28) to assess robustness of Fisher's exact test results.

The rationale for specifying Fisher's exact test for the primary analysis as opposed to specifying the CMH test is because when a stratum has 100% response for 1 treatment group and 0% response for another treatment group, the CMH test may lose efficiency or not be computable. This is evident from the Phase 2 study outcome.

The second co-primary endpoint will be analyzed using mixed model for repeat measures (MMRM) with treatment, week, treatment-by-week interaction, and baseline TSS-by-week interaction as fixed factors; gender and baseline TSS (continuous) as covariates; and study site (with pooling by geographic location) as random effect. If the model does not converge with pooled sites as a random effect, it will be simplified with pooled site as a fixed effect. Details about the method for pooling sites will be provided in the statistical analysis plan (SAP).

The weekly TSS is calculated as the average of the daily TSS. Weekly TSS will be set to missing if >3 daily TSS are missing. Baseline TSS will be the average of the last 2 weeks of daily TSS collected prior to the first infusion. The model variance-covariance matrix will be unstructured. However, if computation does not converge, the matrix will take the form of Toeplitz, autoregressive, or compound symmetry, whichever converges first.

Data on patients who experience an ICE, i.e., exit the study prematurely or initiate prohibited or restricted medications, prior to the end of Week 24 will be set to missing. If it is evident that the

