17.6 Payment to Patients

All patients may be compensated for participating in this study, in accordance with the payment amounts per study day stated in the patient's signed ICF approved by the IRB. If the patient is discontinued from the study prior to the last study visit, the patient will be compensated for each completed study visit on a pro rata basis, as stated in the patient's ICF. Beginning at dosing Day 1, Patients will be compensated for each completed week of daily questionnaires as long as at least 4 questionnaires per week are completed. After randomization, patients at participating study sites may be reimbursed for expenses associated with attending study visits. No additional compensation beyond what is stated in the ICF is permitted.

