Appendix 7: ePRO Teaching Tool cont.

ePRO Teaching Tool: Study AK002-021 (continued)

IT IS IMPORTANT:

- You complete AS MANY daily questionnaires as possible.
- You think about your symptoms in the same way throughout the whole study, which includes before, during and after receiving the study drug.
- You remember that each symptom should be assessed over the past 24 hours (1 day).
- You hit SEND after you have finished all questions on each questionnaire.
- You hit GO TO STARTPAGE to see if there are any additional questions that need to be answered for that day.

STUDY COORDINATORS – COMPLETE THIS UPON VIEDOCME ACTIVATION:

Questionnaire Website: <https://v4me.viedoc.net>

Username: _____

PIN (do not share with others): _____

Daily questions to answer: Use the table below to demonstrate which questions should be completed:

QUESTIONNAIRE	Screening	During Study
EG/EoD PRO questionnaire – (10) questions	X	X
Sf-36 Health Survey "Your Health and Well-Being"	X	X (ONLY DURING STUDY VISITS)
Additional Question – {1} question each	Screening	During study
Dysphagia question	X	X
Constipation question	X	X

*Additional questions for dysphagia and constipation will populate only AFTER you have completed the daily EG/EoD questionnaire.

You must hit SEND and GO TO START PAGE to see all questionnaires.

START DIARY TODAY!

Additional Information regarding diary completion on Page 4

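### The diary training sheet tells patients that symptom intensity bears on enrolment, an avoidable reason to over-report before the TSS baseline is taken

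*Protocol*

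**What the plan says.** Section 12.1, item 7, makes the training sheet a step of diary activation: "Use the ePRO Teaching Tool to instruct the patient on use of the electronic platform". The sheet (Appendix 7) tells patients that during screening "the questionnaire is used to determine if your symptoms are appropriate in type and intensity to be enrolled into the study".

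That diary has three later uses:

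- **Eligibility.** Section 7.4, criterion 5, requires pain, nausea or diarrhea of at least 3, and "a weekly average TSS of ≥ 10 for at least 2 weeks of screening". Both are minimums, with no upper limit.
- **Stratum.** Section 10.2: "The site will enter the highest weekly TSS of disease activity recorded during the screening period", split at 28.
- **Baseline for the second co-primary endpoint.** Section 15.6.1: "Baseline TSS will be the average of the last 2 weeks of daily TSS collected prior to the first infusion".

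The sheet also contains some counterweight. It asks that "You think about your symptoms in the same way throughout the whole study, which includes before, during and after receiving the study drug", and it tells patients to answer each question as well as they can. It does not state the TSS or item cut-offs.

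**The concern.** A patient who wants to enter is told, as the diary starts, that its intensity scores are part of the entry test. Under the symptom criteria a higher score can only help. The documents show ordinary reasons to want entry: no approved treatment exists, open-label AK002 is offered after six doses, and Section 17.6 says "Beginning at dosing Day 1, Patients will be compensated for each completed week of daily questionnaires". No run-in or separate baseline period is described that would keep the qualifying scores apart from the baseline scores.

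If some patients score high to qualify and then score normally, the recorded TSS falls in both arms without any true change. At stake is the sensitivity of a subjective co-primary endpoint. The comparison between arms remains valid. Nothing in completing the diary depends on the sentence.

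**Working it through.** **Inputs.** From Protocol 15.1: 40 per arm, difference 7.4, SD 12.5, stated power 80%. From SAP 5.8: two-sided 0.05. The amount and pattern of inflation are not in the documents, so every figure after step 1 is an illustration.

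**1. The plan's own figure.** Power ≈ Φ(δ / (σ√(2/n)) − 1.96). The standard error is 12.5 × √(2/40) = 2.795. Then 7.4 / 2.795 = 2.648, and Φ(0.688) = 75.4%. The t-distribution gives 74.4%. The stated 80% does not reproduce; it needs 45 per arm (normal) or 46 (t). This is a separate matter, but it means there is no spare power. No allowance for dropout or for removing the Excluded population is stated.

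**2. Uniform inflation, additive effect.** If every patient's baseline is k points too high, both arms' change shifts by −k and the difference is untouched. In a model adjusted for baseline TSS, the constant goes into the intercept. A simulated ANCOVA on observed baseline (assumed true baseline mean 28, SD 10; placebo change −8; residual SD 12.5; 6,000 replicates) gave power of 73% with no inflation and 74% with 3 points for everyone, which is the same within simulation error. The mean placebo change moved from −8.0 to −11.0.

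**3. Inflation that varies between patients.** With between-patient SD s, the SD of change becomes √(12.5² + s²).

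| s | SD of change | Unadjusted power |
|---|---|---|
| 0 | 12.5 | 75% |
| 3 | 12.9 | 73% |
| 5 | 13.5 | 69% |
| 7 | 14.3 | 64% |

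In the same ANCOVA simulation, inflation drawn with mean 3 and SD 3, mean 5 and SD 5, or mean 6 and SD 8 (negative draws set to zero) gave power of 73%, 70% and 66%.

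**4. Patients who qualify only by inflation.** If a fraction f enters this way and shows no drug effect, the difference is 7.4 × (1 − f), with SD kept at 12.5.

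| f | Difference | Power |
|---|---|---|
| 0 | 7.40 | 75% |
| 5% | 7.03 | 71% |
| 10% | 6.66 | 66% |
| 20% | 5.92 | 56% |
| 30% | 5.18 | 46% |

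**5. Responder endpoints.** These divide by baseline and use Fisher or CMH tests without continuous baseline TSS (Protocol 15.6.2; SAP 6.12.3 and 6.12.4), so even uniform inflation reaches them. A patient with a true TSS of 20 who reports 25 shows (25 − 20)/25 = 20% improvement with no real change. That patient meets the 50% criterion at 12.5, a true fall of 7.5 points where 10 would have been needed. Response rates rise in both arms.

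**6. Type I error.** Scores are given before double-blind randomisation, so inflation is balanced between arms in expectation. Simulated type I error was 5.1% to 5.9% over the five settings (5.2% with no inflation). The simulation standard error is √(0.05 × 0.95 / 3,000) = 0.4 points.

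**The case against.** The case against acting has force. The sentence speaks of appropriate type and intensity. It does not say that higher is better and it gives no eligibility cut-off. Symptoms alone do not decide entry, because central histology is a separate requirement. The TSS minimum of 10 is low beside AK002-016 mean baselines of 29.5 and 27.57, so a typical patient would need no inflation to qualify. The sheet already asks for consistent, best-effort answers. The consent text is not available here; if it also explains symptom eligibility, removing one line changes less. All of this stands and limits the likely size. It does not remove the one-way incentive, since the existing instructions are general and sit beside a statement that intensity counts for entry.

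Three stronger inferences are tempting, and the documents do not support them.

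- **That inflation explains the AK002-016 result.** On Table 1's "Symptom Endpoint: Absolute mean change in subject reported TSS", placebo fell 11.5 from 27.57, or 41.7%, against 24% for placebo in Phase 2. The synopsis gives the Phase 2 figure for TSS8 after four monthly doses, while AK002-016 used TSS6 at Weeks 23–24. Nothing says that AK002-016 used this sentence. The protocol points instead to differences between sites (Section 2.3) and to confounding conditions (Section 4.5.1).
- **That average inflation of a few points must cost power.** If the drug effect were proportional to true burden, 5 points would cut the difference to 7.4 × (28.52 − 5)/28.52 = 6.1 and t-test power to 58%. That proportionality is not in the documents. The calculation also scales an effect planned from AK002-003, whose TSS baseline is not given, by the pooled AK002-016 baseline, (89 × 29.5 + 91 × 27.57)/180 = 28.52, in a population with EG and/or EoD.
- **That the comparison is biased toward AK002.** Randomisation after screening rules this out in expectation.

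**Conclusion.** The point holds as an avoidable threat to sensitivity. Its facts are certain: the wording, its use in training every patient, the minimum-only symptom criteria, and the shared diary. Its size is not known. The loss of power is zero under uniform inflation with an additive effect. It becomes material only if inflation is uneven or brings in patients who would not otherwise qualify; 10% of patients of that kind, with no drug effect, would take power from about 75% to 66%. The low TSS minimum suggests that the real loss may be modest. The percent-reduction responder rates can be raised even by uniform inflation, in both arms. Because the TSS endpoint starts at about 74–75% power rather than 80%, even a small avoidable loss is worth preventing. This is a cheap improvement and not a flaw in the validity of the comparison.

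**What to change.** - Delete the sentence on enrolment from Appendix 7.
- Keep the existing instructions on thinking about symptoms consistently and answering as well as possible. Add one neutral line that there are no right or wrong answers.
- State in Section 12.1 that site staff do not tell patients the symptom score cut-offs, as far as informed consent allows.

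The cost is one revised patient-facing page and one added line in Section 12.1, submitted to the IRB. The data collected and the analysis do not change. If enrolment has begun (the documents do not say), earlier and later patients will have been trained on different wording, so the date of the change at each site should be recorded.
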